#### **7.4.1 Subgroup Analyses**

Prespecified subgroup analysis of the primary composite endpoints in patients with 4 points on the OCT calcium score defined by Fujino et al. [4]. In order to have 4 points the patient must have presence of all 3 criteria: maximum calcium angle  $>180$  degrees, maximum calcium thickness of  $> 0.5\text{mm}$ , and calcium length  $> 5.0\text{mm}$ . Consequently, we exclude the patients who

- do not have any OCT during index admission
- patients who have less than 4 points on the score

Within this subgroup we will perform the primary analysis and any secondary analyses that are possibly given the subgroup. If the subgroup is small and events become rare, we will use exact methods to avoid type I error rate inflation.

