### 3.1.3 Exploratory

There are several exploratory endpoints:

- Procedural endpoints
  - Complications (many)
  - Procedure details (durations/doses etc)
  - Procedure cost
- OCT endpoints at index procedure
  - Stent malapposition
  - Calcium disruption
- OCT endpoints at 1 year
  - In-segment late lumen loss
  - In-segment re-stenosis
  - Stent malapposition
- Symptom status at 1 year

Here, we do not specify a hypothesis, as we will also not report p-values from any exploratory analysis.

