### 5 Multiplicity Adjustment

No multiple testing correction will be used, as formal hypothesis testing will be performed only for the primary endpoint/estimand described in Section 3.1.1, for the null hypothesis defined in Section 7.1.1.

Reporting for other endpoints/estimands will either be limited to point estimates of effects with 95% (two-sided) confidence intervals, or p-values will be noted explicitly as secondary. The widths of the intervals will not be adjusted for multiplicity; therefore, it will not be possible to use them in place of formal hypothesis testing. This is in line with current recommendations [8].

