## 8 Sample Size Determination and Power Calculation

In the protocol, it was stated that to reach 80% power to detect a true difference of 15%, with 25% in the standard of care group and 10% events in the IVL group for a two-sided test with alpha of 0.05, 194 patients total, 97 per arm, are needed when randomized 1:1. However, it was planned to enroll 200 patients to allow for a low level of loss to follow-up.

Instead, when using the intended exact method, we find that 194, 97 per arm, only provides 78% power for the hypothesized true difference in risks. Using the intended enrollment of 100 per arm, we reach the desired 80% power. These power calculations were carried out using the Power2x2 function, as outlined below.

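### The calcium subgroup repeats the primary analysis in 4-point patients alone, with no estimate in lower-score patients and no contrast, and the status of its p-value is unclear

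*SAP*

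**What the plan says.** Section 7.4.1 prespecifies an analysis of the primary composite in patients with the full 4 points on the OCT calcium score. Patients with a lower score, and patients without OCT during the index admission, are excluded from it. It continues: "Within this subgroup we will perform the primary analysis and any secondary analyses that are possibly given the subgroup". It adds that exact methods will be used if events become rare, so as not to inflate the type I error rate, which suggests that a test is in mind.

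The primary analysis in Section 7.1.1 consists of a risk ratio, a 95% CI, a matching p-value, and a rule that reads p ≤ 0.05 with a ratio below 1 as evidence of superiority.

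Two other sections bear on the p-value. Section 5 says "formal hypothesis testing will be performed only for the primary endpoint/estimand described in Section 3.1.1", and then allows other results to be given as estimates with intervals or with p-values marked as secondary. Section 3.1.3 says "we will also not report p-values from any exploratory analysis". The subgroup section stands under heading 7.4, which covers exploratory endpoints.

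The only treatment interactions in the SAP are in Section 7.1.2. They concern presentation, prior revascularization, diabetes and LAD location, and serve to obtain standardized marginal risk ratios. The calcium score is not among them.

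**The concern.** Calcium severity is the only feature that selects these patients, so readers will ask whether the effect differs by severity. An analysis inside one stratum cannot answer that. Its p-value depends heavily on how many patients fall in the stratum. A significant result invites the reading that IVL works especially well in severe calcium, and a non-significant one that it does not work there. Neither follows without the matching estimate in lower-score patients and a comparison of the two.

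Separately, one analyst could follow Section 7.4.1 with Section 5 and print a p-value labelled secondary, while another could follow Section 3.1.3 and print none. A prespecified analysis should not leave that to choice.

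**Working it through.** **Inputs from the SAP (Section 8).** Event risks are "25% in the standard of care group and 10% events in the IVL group", "for a two-sided test with alpha of 0.05". The chi-squared basis was "194 patients total, 97 per arm, are needed when randomized 1:1". With the exact test, 97 per arm "only provides 78% power for the hypothesized true difference in risks", and "Using the intended enrollment of 100 per arm, we reach the desired 80% power".

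**Assumptions.** The share of patients with 4 points is not stated. I take 40%, 50% and 60% of 100 per arm, split equally between arms, with every patient scored and the endpoint known. The effect is taken as 25% v 10% in every patient, so there is no effect modification.

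**Step 1: reproduce the plan's figures.**
- Unpooled normal formula: n = (0.25×0.75 + 0.10×0.90) × (1.96 + 0.842)² / 0.15² = 0.2775 × 7.85 / 0.0225 ≈ 96.8, so 97 per arm. This matches.
- The unconditional exact test was recoded (mid-p Fisher ordering, p maximised over a grid of the common risk, two-sided p equal to twice the smaller tail) and power summed over all 2×2 tables. It gives 78.2% at 97 per arm and 80.3% at 100 per arm. Both match.

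**Step 2: the same test inside the subgroup.**

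| Share with 4 points | Per arm | Power | Not significant (1 − power) |
|---|---|---|---|
| 40% | 40 | 38.7% | 61.3% |
| 50% | 50 | 48.7% | 51.3% |
| 60% | 60 | 57.9% | 42.1% |

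Over a wider range of shares, 30% gives 27.3% power and 70% gives 63.5%. So even when severity makes no difference at all, the subgroup test misses in roughly 42-61% of trials at shares of 40-60%.

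**Step 3: precision of a contrast between strata.** The variance of the log risk ratio in a stratum of n per arm is
(1 − 0.25)/(0.25n) + (1 − 0.10)/(0.10n) = 3/n + 9/n = 12/n.
- 50 per arm in each stratum: 12/50 + 12/50 = 0.48; 1.96 × √0.48 = 1.358; exp(1.358) ≈ 3.9.
- 40 and 60 per arm: 12/40 + 12/60 = 0.50; 1.96 × √0.50 = 1.386; exp(1.386) ≈ 4.0.

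The 95% CI for the ratio of risk ratios is therefore about the estimate times or divided by 3.9 to 4.0.

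**Step 4: power of that contrast in an extreme case.** Take 25% v 10% in 4-point patients and no effect (25% v 25%) in the rest. For shares of 30%, 50% and 70%, power is about 26%, 33% and 32% on the log risk ratio scale, and 24%, 26% and 22% on the risk-difference scale. The contrast is useful as an estimate, not as a test.

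**The case against.** - **No effect-modification aim is stated.** This stands. The SAP nowhere says that the subgroup is meant to show dependence on calcium severity, and it can be read as estimation in a more severely calcified population. If so, the test adds nothing to the estimate and interval, and reporting the other stratum still guards against over-reading.
- **Section 5 already prevents formal inference.** A reader might infer that Section 7.4.1 flatly contradicts Section 5. It does not: Section 5 allows p-values outside the primary estimand if they are labelled secondary. Section 3.1.3 is the harder passage to square, but it introduces the exploratory endpoints, and the subgroup concerns the primary endpoint and is exploratory mainly by its place under 7.4. What remains is an ambiguity. Section 7.4.1 neither applies the secondary label nor says whether the superiority rule of 7.1.1 comes with the repeated analysis.
- **Lower-score patients are not lost.** A reader might infer that they are never analysed. They remain in the primary analysis if their endpoint is complete, and Section 7.4.5 plans descriptive outcome summaries in relevant subgroups. But that section does not name this group, and a descriptive summary is not a contrast.
- **Low power is true of any subgroup in a trial of 200.** Granted, and the contrast is weaker still. That is a reason to present estimates with intervals instead of a significance result.

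**Conclusion.** The point holds as a matter of design and reporting. As written, the subgroup result cannot be read, in either direction, as evidence that the effect depends on calcium severity. Under a uniform 25% v 10% effect and an assumed 40-60% share, the subgroup test has about 39-58% power, so a non-significant result would be unremarkable. The exact figures depend on the assumed share; the absence of a comparator stratum does not. The status of the subgroup p-value is unclear between Sections 3.1.3, 5 and 7.4.1.

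Two stronger readings are not supported. The SAP does not announce a formal superiority claim in the subgroup, since Section 5 confines formal testing to the primary estimand. Nor can the harm be measured by how often subgroup and complement would disagree on significance, because no test in the complement is planned. The primary conclusion is unaffected.

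**What to change.** In Section 7.4.1:

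1. Report the risk ratio with 95% CI in 4-point patients and in OCT-scored patients with fewer than 4 points. State that patients without index OCT belong to neither group, and give their number.
2. Report the ratio of the two risk ratios with 95% CI as exploratory estimation. Name the method, for example the difference of stratum-specific log risk ratios, or standardization as in Section 7.1.2. A logistic arm-by-score term alone gives a ratio of odds ratios and would not do. With about 0.10 × 50 = 5 expected IVL events in a stratum of 50 per arm, say in advance what is done if a cell has no events.
3. State that the superiority rule of Section 7.1.1 does not apply to the subgroup and that no subgroup p-value is reported, in line with Section 3.1.3.

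The cost is a few lines of SAP text and one further contrast on data already collected. The downside is a wide interval for the contrast, roughly a factor of 3.9 each way at 50 per arm per stratum, which should be stated with the result.

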#### **7.4.2 Timing of Follow-up Visits**

Descriptive statistics, per arm, will be presented for the time from randomization to the “12-month” follow-up visit (which will possibly be slightly less or more than 12 months for all patients). Median, minimum, maximum, first and third quartiles will be reported. An exploratory analysis of time to the “12-month” visit will be performed to ensure that there is no significant difference in timing by arm.

#### **7.4.3 Recruitment**

Recruitment of the patients will be summarized via descriptive statistics. Especially, start and end dates of recruitment will be presented as well as a flowchart, inspired by the CONSORT guidelines and template [10].

#### 7.4.4 Descriptive Statistics of Baseline Characteristics

Baseline characteristics will be descriptively summarized, within each of these four groups: randomized each arm within the main analysis set A and each arm among any patients that do not complete follow-up. The list of baseline variables to be summarized includes the variables outlined in Table 1.

Table 1: Table 1 draft

Age, yrs	mean(SD)
Women	Freq (%)
Acute coronary syndrome	Freq (%)
NYHA >2	Freq (%)
CCS >2	Freq (%)
Ejection fraction	Freq (%)
BMI	kg m-2
Medical history	
Diabetes mellitus	Freq (%)
Hypertension	Freq (%)
Current smoker	Freq (%)
Renal insufficiency	Freq (%)
Myocardial infarction or coronary revascularization	Freq (%)

For continuous variables, we will present median, first and third quartiles and also minimum and maximum. Categorical variables will be summarized by numbers and percentages. Hypothesis tests will not be performed to compare baseline characteristics, but clinical importance of any apparent imbalance will be noted. This is in line with usual recommendations [9].

#### 7.4.5 Descriptive Statistics of Outcomes

Outcomes (primary, secondary and exploratory) will also be descriptively summarized, within relevant subgroups. Similar descriptive statistics as for baseline characteristics will be used. Mean and standard deviation will be presented instead of median, first and third quartiles (or in addition to those) whenever appropriate. For each outcome.

#### 7.4.6 Consort data

Available data about enrollment, protocol adherence and follow-up will be presented in a flow diagram, following the CONSORT guidelines [10].

### 7.5 Changes to Protocol-Planned Analyses

- The power calculations are changed from the protocol as outlined below, the original analysis was planned as a chi-squared test, but the rate of events may be too low for this to have correct type I error rate. Thus, we will use an exact test to strongly control type I error. The new power calculations are given in Section 8, below.

## 8 Sample Size Determination and Power Calculation

In the protocol, it was stated that to reach 80% power to detect a true difference of 15%, with 25% in the standard of care group and 10% events in the IVL group for a two-sided test with alpha of 0.05, 194 patients total, 97 per arm, are needed when randomized 1:1. However, it was planned to enroll 200 patients to allow for a low level of loss to follow-up.

Instead, when using the intended exact method, we find that 194, 97 per arm, only provides 78% power for the hypothesized true difference in risks. Using the intended enrollment of 100 per arm, we reach the desired 80% power. These power calculations were carried out using the Power2x2 function, as outlined below.

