## 6 Analysis Sets

- The “**Main analysis set A**” consists of all randomized participants who have a complete measure of the primary composite endpoint. This will exclude three groups of patients: patients who withdraw consent prior to 1 year and explicitly do not wish to participate in the 1-year clinical follow-up data collection, patients that are deemed to be lost to follow-up by the Clinical Endpoint Adjudication Board (see section 4.3 of protocol version 5.3), and patients who lack baseline OCT or Quantitative coronary angiography.
- The “**Sensitivity analysis set or Main analysis B**” consists of all randomized participants.
- **Secondary Safety endpoint analysis set 1, 1a, 1b, 1c:** consists of all randomized participants who have a measure of in-hospital and 1 year major adverse cardiac events for set 1, all randomized participants who have a measure of Cardiac death at or before one year after the index procedure, 1a, all randomized participants who have a measure of any myocardial infarction at or before one year after the index procedure, 1b, and all randomized participants who have a measure of stroke at or before one year after the index procedure, 1c.
- **Secondary Safety endpoint analysis set 2, 2a, 2b, 2c:** consists of all randomized participants who have a measure of in-hospital procedure events overall, 2, of periprocedural myocardial infarction, 2a, coronary dissection (beyond intended by lesion preparation), 2b, and coronary perforation/rupture, 2c. As it is very likely that all randomized participants will have measures of these events or be followed to know that the event did not occur, all of these groups may be the same as “Sensitivity analysis set or Main analysis B”

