### 7.1.2 Sensitivity Analyses

**For missingness** The main analysis is based on the “Main analysis set A”, which does not include patients for whom the primary endpoint is missing. This choice may be anti-conservative if the reason for drop-out was related to the outcome and differed between arms. For this reason, we will use the causal bounds from Gabriel et al. [5] for the effect given in equation 2 and the best-case/worst-case bounds equation 3 of the same paper if there are any missing composite outcome values based on “Main analysis set B” detailed in Section 6. If there is additional noncompliance, we will use the equivalent bounds for the per-protocol effect, as this can sometimes give large intervals. Given the conservative nature of the bounds, we will not further place confidence intervals on them unless it is deemed necessary for publication, in which case exact confidence intervals will be used.

**For mechanistic imputation** The composite outcome may have some form of “mechanistic” imputation, i.e. residual area stenosis  $>20\%$  is determined by direct measurement (OCT) of, if necessary, by quantitative coronary angiography. Values indicating residual area stenosis  $>20\%$  from OCT or angiography are considered reliable, however, particularly with quantitative coronary angiography, missing OCT analysis due to poor image quality or failure to obtain OCT is possible and may be related to residual area stenosis. Thus, we will impute all “mechanistic” imputed residual area stenosis that were found to be  $<20\%$  to be  $>20\%$  to determine the impact that missed OCT analyses could cause. Additionally, all patients without true measure of no event, that were adjudicated to have no event for the primary analysis, will instead be imputed to have an event and the impact of the adjudication will be determined by rerunning the primary analysis.

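### The 80% power in SAP Section 8 requires all 200 enrolled patients to be analysed; at the plan's own allowance for loss (194 analysed) it is about 78% to 79%.

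*SAP*

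**What the plan says.** Section 8 of the SAP recalls the protocol's calculation: event risks of 25% under standard care and 10% under IVL, a two-sided 5% level and 80% power lead to a requirement of 194 patients. It then explains the enrolment target: "it was planned to enroll 200 patients to allow for a low level of loss to follow-up". The margin is therefore 200 − 194 = 6 patients.

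The next paragraph replaces the chi-squared test with the exact unconditional test and reports that the protocol's sample size "only provides 78% power for the hypothesized true difference in risks". The section's conclusion on power is: "Using the intended enrollment of 100 per arm, we reach the desired 80% power". Nothing further is said about loss.

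Section 7.1.1 runs the primary test on Main analysis set A. Section 6 removes three groups from that set: patients who withdraw and decline 1-year data collection, patients judged lost to follow-up, and "patients who lack baseline OCT or Quantitative coronary angiography". Section 7.1.2 confirms that the main analysis uses a set "which does not include patients for whom the primary endpoint is missing".

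**The concern.** The same six patients do two jobs. In the first paragraph of Section 8 they are the reserve that may be lost while 194 remain for analysis. In the second they are analysed patients who lift power from 78% to 80%. Both cannot hold unless no one is excluded from set A, and Section 8 does not state that condition.

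The power code in Section 9.1 takes n1 and n2 as the numbers entering the test, so 100 and 100 means complete endpoint data in both arms. Set A can also lose patients for lack of baseline imaging, which is separate from the loss to follow-up that the 200 was meant to cover.

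What is at stake is the accuracy of a planning figure. Section 7.5 lists the new power calculation as a change from the protocol. A reader would take its result, 80%, as the power of the design with its allowance for loss still in place.

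**Working it through.** **Inputs (SAP Section 8, test from Section 9.1).** Event risks 10% (IVL) and 25% (control); two-sided alpha 0.05; 194 needed; 200 enrolled, 1:1; unconditional exact test, ratio parameter, FisherAdj ordering, no mid-p correction of the p-value.

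**Protocol basis.** The unpooled formula gives

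n per arm = (1.960 + 0.842)² × (0.25 × 0.75 + 0.10 × 0.90) / 0.15² = 96.8, so 97.

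The exact power of the chi-squared test at 97 per arm is 80.2%. The 194 is reproduced.

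**Exact test.** Power = Σ Bin(x1; n1, 0.10) × Bin(x2; n2, 0.25), summed over all tables with p ≤ 0.05. Tables were ordered by Fisher mid-p (the reading taken of FisherAdj). The one-sided p-value was maximised over a common risk on a grid of about 1000 points and doubled. This was done by full enumeration in Python; the R package was not run.

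| Analysed (IVL/control) | Power | SAP figure |
|---|---|---|
| 97/97 | 78.2% | 78% |
| 100/100 | 80.3% | 80% |

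Both printed figures reproduce. Ordering by the ordinary Fisher p-value instead gives 77.5% and 79.2%, and Fisher's conditional test gives 74.6% and 76.2%. Neither matches the SAP's 80%, which supports the reading used.

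**Power after exclusions.** Starting from 100/100, k patients are removed in every possible split between arms. The average weights each split by its hypergeometric probability, as if exclusions fell at random.

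| Excluded k | Analysed | Range over splits | Average |
|---|---|---|---|
| 0 | 200 | 80.3% | 80.3% |
| 1 | 199 | 80.3% to 80.5% | 80.4% |
| 2 | 198 | 79.5% to 79.9% | 79.7% |
| 3 | 197 | 79.9% to 80.6% | 80.1% |
| 4 | 196 | 78.7% to 79.5% | 79.0% |
| 5 | 195 | 79.3% to 79.98% | 79.5% |
| 6 | 194 | 78.2% (97/97) to 79.1% (100/94) | 78.5% |
| 7 | 193 | at most 79.6% | 79.2% |
| 8 | 192 | at most 78.7% | 78.0% |

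The values do not fall steadily because the test is discrete. The allowance implied by the SAP is 6/200 = 3%, the row k = 6. The gap to the 80% target there is 80 − 79.1 = 0.9 to 80 − 78.2 = 1.8 points.

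**Larger loss (an assumption; the SAP gives no such rate).** With 10% excluded equally, 90/90 analysed, power is 76.7%.

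**The case against.** The best reply is that nothing is hidden. The SAP prints 78% for 194 patients, ties the 80% openly to enrolment, and reports the allowance for loss as the protocol's plan, not as a feature of the new calculation. No sum is wrong. The gap is close to the whole-percent precision used: average power is 79.7% with two exclusions, 80.1% with three and 79.5% with five, and six happens to sit at a dip. The SAP also keeps set A broad. Angiography may stand in for OCT, withdrawal excludes only those who also refuse 1-year data collection, non-cardiac death is not treated as missing, and some patients without a true measure are adjudicated as event-free and retained. Six exclusions may therefore never occur.

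Much of this stands. The arithmetic is correct, the shortfall is small, and the number of exclusions is not known in advance. What does not stand is the inference that the section reads correctly as it is. The 78% appears only as the problem that 100 per arm is said to solve, and the closing sentence treats it as solved. That is so only with almost complete endpoint data. Six is the margin the SAP itself gives, so comparing the target with power at 194 imports no outside figure.

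**Conclusion.** The concern holds and is minor. Section 8's 80% is the power with no exclusions from set A. At the plan's own allowance, 194 analysed, power is 78.2% to 79.1%, about 1 to 2 points under the target. Roughly 80% is kept with up to three exclusions; every split of four to eight is below 80%, by as little as 0.02 points in the most favourable case.

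This rests on the SAP's assumed risks of 10% and 25%, on reading FisherAdj as Fisher mid-p ordering (which reproduces both printed figures), and on the 3% loss implied by 194 and 200, since no loss rate is stated. The validity of the test, the estimate and the decision rule is unaffected.

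**What to change.** Restate the end of Section 8 to say that, with the exact test, 100 analysed patients per arm are needed for 80% power; that enrolment of 200 therefore contains no margin for exclusions from set A; and that if the planned allowance is used up (194 in set A) power is about 78% to 79%. Any larger loss that is quoted should be labelled as an assumption.

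The cost is one sentence and a stated power 1 to 2 points less favourable. No change to enrolment or analysis is needed. For scale only, keeping 100 analysed per arm after a 3% loss would take 100/0.97 = 103.1, that is 104 per arm or 208 in total.
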